3.2 Assigning Subjects to Treatment Groups

3.2.1 Subject Numbering

Each subject screened for the study will be assigned a unique subject number that will be used to identify the subject throughout their participation in the study. If a subject fails to be randomized, the reason should be documented in the source documents and case report form (CRF). The subject will be considered a screen failure.

3.2.2 Randomization

Subjects will be randomized 2:1 to receive ADX-102 1% or vehicle through interactive response technology (IRT) at Baseline Visit Day 1.

3.3 Blinding and Unblinding

3.3.1 Blinding

Subjects will be randomized in a double-blind fashion. Investigators, qualified study personnel, subjects, and caregivers will be blinded to the study drug treatment administered. The Sponsor will also be blinded to the study drug treatment administered until database lock (Part 1 and Part 2).

3.3.2 Emergency Unblinding

Emergency unblinding should only be performed when necessary to treat the subject. Most often, knowledge of the possible treatment assignments is sufficient to treat a study subject who presents with an emergency condition.

Unblinding will result in the subject being discontinued from the study, irrespective of whether the Investigator the event is deemed related to study drug.

¹Dorsal foot cannot be selected as the target efficacy area.

There is no known antidote to ADX-102, so symptomatic and supportive management of any suspected and treatment-related adverse event, if necessary, is clinically indicated.

The treatment code for a subject may only be broken by the Investigator or Sponsor for reasons of subject safety or in an emergency when knowledge of the study drug administered would be important for the treatment of the patient. However, the Investigator should make every effort to contact the Medical Monitor to discuss the subject's emergency and the need to unblind, prior to unblinding any subject.

In situations in which the Investigator has tried but is unable to reach the Medical Monitor, the Investigator should use his/her best judgment, based on the nature and urgency of the clinical situation, and may proceed with unblinding without having successfully reached and discussed the situation with the Medical Monitor. Once a subject's treatment assignment has been unblinded, the Medical Monitor should be notified within 24 hours of unblinding of the treatment, without revealing the study treatment.

The blind may be broken in the case of a pregnancy should the subject desire this information.

The date, time and reason for breaking the blind are to be recorded in the subject's CRF and source documents.

In the event of a drug-related, serious, unexpected AE, the Sponsor's Pharmacovigilance Department or designee will be provided with the treatment assignment for the subject for regulatory reporting.

3.4 Safety Oversight

During the study, subject safety will be monitored on a continuous basis by the Medical Monitor until the last subject completes his or her last scheduled study assessment.

3.4.1 Data Safety Monitoring Board

An independent DSMB will be established to review all available safety data after approximately 9 subjects have completed Week 24 in Part 1. The assessment of safety will be determined from dermatological endpoints, vital sign measurements, physical examinations, hematology and chemistry laboratory testing, ECG readings, use of concomitant medications, and review of adverse events. Based on the safety data provided, the DSMB will provide recommendations about stopping or continuing the trial.

The DSMB will be advisory to the Sponsor's clinical trial leadership group Steering Committee which will be blinded during Part 1 until database lock. The Steering Committee will be responsible for promptly reviewing the DSMB recommendations, to decide whether to continue or terminate the trial, and to determine whether amendments to the protocol or changes in study conduct are required.

Additional DSMB reviews will occur approximately every 6 months throughout the trial, or as deemed necessary by the DSMB or Sponsor to ensure subject safety and well-being. Study enrollment and dosing will continue while the DSMB evaluates data. A DSMB charter will be prepared. The charter will contain the required information for the formation, activities, and conduct of the DSMB.

3.5 Study Duration for Individual Subjects

Following the Screening Visit, eligible subjects will enter the study for up to 28 weeks in each Part 1 and Part 2. This comprises of a 24-week study treatment phase followed by a 4-week follow-up period.

4 STUDY POPULATION SELECTION

4.1 Inclusion Criteria

Subjects meeting all the following criteria will be considered eligible for study entry:

- 1. Subject is aged 3 years or older.
- 2. Subject has a genetically-confirmed diagnosis of SLS.
- 3. Subject has active ichthyosis that is Grade 2 or higher on the VIIS scaling severity score.
- 4. Subject or subject's caretaker is willing and able to provide written informed consent prior to the initiation of any study procedures. Assent will be solicited from pediatric subjects capable of providing assent.
- 5. Females of child-bearing potential: Negative pregnancy test at Screening and Baseline Visits.
- 6. Subjects who are sexually active agree to use medically acceptable method (as defined by the Investigator) of birth control as follows:
 - For females: Compliant with a contraceptive regimen if of child-bearing potential during the study, or documented to be surgically sterile or post-menopausal.
 - For males: Compliant with a contraceptive regimen during the study or documented to be surgically sterile.

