1 INTRODUCTION

1.1 Sjögren-Larsson Syndrome

ADX-102 1% is being developed for the treatment of ichthyosis associated with Sjögren-Larsson Syndrome (SLS). SLS (ICD Q87.1) is a rare, chronically-debilitating, autosomal-recessive disorder characterized by generalized ichthyosis, cognitive deficit in a majority of patients, and spastic diplegia or tetraplegia. SLS is caused by mutations in the *ALDH3A2* gene that encodes fatty aldehyde dehydrogenase (FALDH), an enzyme that catalyzes the oxidation of aliphatic aldehydes to fatty acids (3).

In most patients, ichthyosis (dry, thickened, scaly, erythematous skin that is pruritic and, due to frequent excoriation, friable) is moderate or severe, particularly prominent in flexure areas, and involves much of the body surface except the face and glabrous skin (3). The dermal symptoms are generally recalcitrant to therapy, and are associated with significant daily physical and emotional burden and social stigma for patients and caregivers. The cutaneous symptoms are apparent at birth in almost all patients; they become more established by several months of age and remain throughout life (2). Developmental delay, spasticity, and other neurological symptoms become apparent over the first 2 years of life. The onset of neurologic symptoms usually prompts recognition of a diagnosis of SLS rather than another type of ichthyotic disorder (2).

SLS ichthyosis pathophysiology is well understood; fatty aldehydes disrupt dermal function, particularly the epidermal fatty moisture barrier, resulting in pathologic water loss, cutaneous desiccation, and compensatory keratinocytic hypertrophy (1). In epidermal cells, FALDH deficiency results in impaired oxidation of long-chain fatty aldehydes to fatty acids. The consequent accumulation of aldehydes disrupts the normal function and secretion of lamellar bodies and leads to intercellular lipid deposits in the stratum corneum and a defective water barrier in the skin layer, resulting in the cutaneous symptoms of SLS (2).

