3 INVESTIGATIONAL PLAN

3.1 Overall Study Design and Plan

This is a two-part, randomized, double-blind, vehicle-controlled, parallel-group Phase 3 clinical trial with an initial assessment of increasing BSA treatment (Part 1). After the completion of Part 1, a separate set of eligible subjects will be enrolled into Part 2.

Part 1 Design:

Part 1 will evaluate the safety, tolerability, and efficacy of treatment to the affected area of ichthyosis initially on approximately 20% BSA and then increasing up to 90% BSA over 24 weeks of exposure and will confirm an appropriate sample size for Part 2.

Subjects will be consented and screened for eligibility. Approximately 9 subjects will be randomized in a 2:1 ratio to receive ADX-102 1% or vehicle.

Subjects or caregivers will apply study drug (i.e., ADX-102 1% or vehicle) to a treatment area identified by the Investigator.

The initial treatment area will be defined as approximately 20% BSA with Grade 2 or higher on the VIIS scaling severity score, as assessed by the Investigator, and will include one of the body sites as defined in the VIIS tool (target efficacy area).¹ From Week 1 through Week 12, subjects will receive treatment once daily in the initial treatment area only.

If the Investigator determines that there are no safety or tolerability issues at the end of Week 12, the treatment area will increase to all of the affected areas of ichthyosis on one-half of the body (approximately 40-45% BSA in a typical SLS patient). From Week 13 through Week 20, subjects will receive treatment once daily on the expanded treatment area.

If there are still no safety or tolerability issues at the end of Week 20, the treatment area will further increase to all affected areas of ichthyosis on the entire body (approximately, 80-90% BSA in a typical SLS patient). Subjects will receive treatment once daily treatment on all affected areas from Week 21 through Week 24.

Subjects completing the 24 weeks of study drug treatment will then be monitored for an additional 4 weeks for safety.

Subjects who are randomized in Part 1 will not be eligible to participate in Part 2.

¹ Dorsal foot cannot be selected as the target efficacy area.

Part 2 Design:

Part 2 will evaluate the safety, tolerability, and efficacy of treatment to the affected area of ichthyosis on the body (approximately 80-90% BSA in a typical SLS patient) over 24 weeks of exposure.

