5.6 Treatment Administration

The target efficacy and treatment areas will be identified by the Investigator as noted below. The Investigator will apply the initial dose of study drug and at designated timepoints when study drug will be applied to expanded treatment areas. These applications will be observed by the subject and caregiver at the study center. Thereafter, subjects or caregivers will apply subsequent doses throughout the duration of the study.

A standard amount of study drug for the percent BSA under treatment will be measured and applied to the treatment area once daily to achieve a dose of approximately 8 mg/cm², with each application administered approximately 24 hours apart. Study drug should only be administered to the treatment area, as directed by the Investigator, during the study.

Subjects or caregivers are required to wear protective gloves during application and thoroughly wash their hands after application to prevent study drug exposure.

At scheduled study visits at the site, subjects may not bathe or apply study drug or as-needed topical symptom control therapy (emollients) to the treatment area within 12 hours of examination or photographic assessment. Subjects should refrain from applying as-needed topical symptom control therapy and bathing within 4 hours of applying study drug to the treatment area. The treated area should be covered by loose clothing to minimize light exposure.

Target Efficacy Area used for the primary endpoint assessment in Part 1 and Part 2 will be based on one of the body sites as defined in the VIIS tool (upper back, upper arm or lower leg/shin)¹ that has a VIIS scaling severity score of Grade 2 or higher as assessed by the Investigator. The body

¹ Dorsal foot cannot be selected as the target efficacy area.

site with the worse VIIS scaling severity score should be selected, if applicable. The target efficacy area will be used for all efficacy analyses.

Treatment Area will be determined by the Investigator as follows:

In Part 1, the initial treatment area will be defined as approximately 20% BSA with Grade 2 or higher on the VIIS scaling severity score, on one-half of the body, left or right side, and will include the target efficacy area. From Week 1 through Week 12, study drug will be applied in the initial treatment area.

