6.9 Visual Index for Ichthyosis Severity

The Investigator will utilize the VIIS tool to evaluate the scaling and erythema components of ichthyosis in each body site/region (upper back, upper arm, lower leg/shin, and dorsal foot) as define in the VIIS scale.

At baseline, two Investigators should administer the VIIS in Part 2.

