7.3. MODIFIED INTENT-TO-TREAT (M-ITT) POPULATION

The modified-Intent-to-Treat (m-ITT) Population will include all randomized subjects from the SAF who received at least one dose of study drug and have at least one VIIS assessment post visit 2. Subjects will be analyzed according to randomized treatment. Unless otherwise specified, efficacy analysis will be performed on this population.

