10.1. PRIMARY EFFICACY ENDPOINT AND ANALYSIS

The primary endpoint for the clinical trial is change from baseline in the VIIS scaling score in drug-treated subjects, as assessed by the investigator, in the target efficacy area. The VIIS provides five-point Likert scales (range 0-4) for erythema and scaling that increases in severity with increasing score values.

The target efficacy area for all efficacy analyses will be one of the body sites as defined in the VIIS tool (with the exception of Dorsal foot) with Grade 2 or higher on baseline VIIS scaling score as assessed by the Investigator.

The within-group change from baseline will be the primary focus of interest in the primary analysis.

Syneos Health #1009367

Primary Analysis

A Mixed Model Repeated Measures (MMRM) model will be used to perform the primary analysis of the VIIS scaling score in drug-treated subjects (not vehicle-treated subjects). Change from baseline VIIS scaling score will serve as the dependent variable. The model will include the baseline value (Visit 1) as a covariate (if useful) and visit (treated as a factor; the visit term will cover Visit 1, 5, 7, and 8). An unstructured covariance structure will be assumed and a Type III model will be evaluated. If the unstructured covariance structure matrix results in a lack of convergence, then Toeplitz (TOEP), first-order autoregressive (AR1), compound symmetric (CS) covariance structure will be used in that order. If the MMRM model cannot hit convergence with any correlation structure, then a within-subject t-test (baseline-adjusted, if useful) will be used to compare baseline to Visit 8. It should be noted that improvement will be signified by the existence of a negative change score.

The primary efficacy endpoint will be summarized descriptively by visit and across all visits. The table will contain descriptive statistics on observed values and change from baseline at each time point.

The primary analysis using the MMRM model will be summarized in a consolidated table containing the following:

- Descriptive statistics for change scores at baseline and each post-treatment time point.
- The LS mean change scores with accompanying standard errors and 95% confidence intervals for each visit.
- Within-group contrasts for each given visit.
- Significance levels for the visit effects.

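### Inclusion criterion 3 names no body site, so a subject with Grade 2 scaling only on the dorsal foot can be randomised without a valid target efficacy area

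*Protocol*

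**What the plan says.** **Entry.** Protocol 4.1, criterion 3, repeated in the synopsis: "Subject has active ichthyosis that is Grade 2 or higher on the VIIS scaling severity score". It names no site.

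**What the VIIS scores.** Protocol 6.9 has the Investigator score scaling and erythema "in each body site/region (upper back, upper arm, lower leg/shin, and dorsal foot"). The collection form in SAP 20.2 lists the same four sites, left and right.

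**Where the primary endpoint may be read.** Protocol 5.6 bases the target efficacy area on "one of the body sites as defined in the VIIS tool (upper back, upper arm or lower leg/shin"), at Grade 2 or higher. A footnote in Protocol 3.1 adds: "Dorsal foot cannot be selected as the target efficacy area". SAP 10.1 agrees, allowing any VIIS site "with the exception of Dorsal foot) with Grade 2 or higher on baseline VIIS scaling score as assessed by the Investigator".

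**How the area is used.** Protocol 5.6: "The target efficacy area will be used for all efficacy analyses".

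**Route to randomisation.** Protocol 6.17 randomises once eligibility is confirmed. The Baseline lists (Protocol 7.2 and 8.2) place eligibility review and the VIIS ahead of randomisation on the same day.

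**Treatment area (Protocol 5.6).** In Part 1 the initial area of roughly 20% BSA has to contain the target efficacy area. In Part 2 it is all affected skin, with no reference to the target area.

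**The concern.** The entry rule and the endpoint rule use the same grade threshold on different sets of sites. Criterion 3 can be met at any of four VIIS sites, while the endpoint is defined at three. The difference is the dorsal foot, and a subject who reaches Grade 2 only there falls between the two rules.

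Neither document says what to do with that subject. The subject might contribute nothing to the primary analysis. Or the subject might be scored at an allowed site of Grade 0 or 1, contrary to the definition. A Grade 0 site cannot improve, and a Grade 1 site can improve by one unit only by clearing completely. With about 20 active subjects in Part 2, one subject is 1/20 = 5% of the arm.

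**Working it through.** **Step 1. Trace a foot-only subject** (dorsal foot Grade 2; upper back, upper arm and lower leg Grade 0 or 1 on both sides; otherwise eligible).

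| Rule | Result |
|---|---|
| Criterion 3 (Protocol 4.1) | Met: Grade 2 at a VIIS site |
| Exclusion criteria (Protocol 4.2) | None concerns the lack of an allowed site |
| Randomisation (Protocol 6.17) | Proceeds once eligibility is confirmed |
| Target efficacy area (Protocol 3.1, 5.6; SAP 10.1) | None exists |
| Part 1 initial treatment area (Protocol 5.6) | Cannot be defined, since it must contain the target area |
| Part 2 treatment area (Protocol 5.6) | Can be defined: all affected skin |
| Part 1 efficacy population (SAP 7.3) | Asks for dosing and that subjects "have at least one VIIS assessment post visit 2"; no valid target area required |
| ITT population (Protocol 10.2) | Asks for a dose and any post-dose assessment; no valid target area required |

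**Step 2. Reproduce the planned power.** Inputs from Protocol 10.1: n = 20 active subjects, mean change 0.5 in size, SD 0.6 or 0.7, two-sided one-sample t-test, alpha 0.05. The noncentrality is (mean / SD) × √n, and power comes from the noncentral t distribution with n − 1 degrees of freedom. The critical value for 19 df is 2.093.

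- SD 0.6: 0.5/0.6 × √20 = 3.727, power 94.2% (stated: 94%).
- SD 0.7: 0.5/0.7 × √20 = 3.194, power 85.8% (stated: 85%).

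The plan's figures reproduce.

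**Step 3. One of the 20 active subjects has no primary endpoint** (n = 19, critical value 2.101).

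- SD 0.6: 0.5/0.6 × √19 = 3.632, power 93.0%.
- SD 0.7: 0.5/0.7 × √19 = 3.113, power 83.7%.

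**Step 4. The subject is kept, scored at a Grade 0 site with zero change** (n = 20).

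- Mean: 0.95 × 0.5 = 0.475.
- Variance of the mixture: 0.95 × SD² + 0.05 × 0.95 × 0.5².
- SD 0.6: 0.342 + 0.011875 = 0.353875, mixture SD 0.595, power about 92%.
- SD 0.7: 0.4655 + 0.011875 = 0.477375, mixture SD 0.691, power about 83%.

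Step 4 is approximate, because a mixture is not normally distributed. All these figures concern the t-test on which the sample size was built, not the full three-part claim rule in Protocol 10.4. The count of one subject is an assumption.

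**The case against.** The best answer is that Baseline procedure already deals with this. The VIIS and the eligibility review come before randomisation. SAP 8.4 says the Part 1 VIIS is completed before randomisation on Day 1, and the collection form wants the selected site scored first. An investigator who looks for an allowed site at Grade 2 and finds none would notice. In Part 1 such a subject could not even be dosed as written. This stands as far as it goes, so it would be wrong to infer that nothing reveals the problem before randomisation. But revealing it is not barring entry: the subject still meets every criterion. Exclusion criterion 9 gives the Investigator discretion over conditions that compromise interpretation, but it is not a rule about scoring sites.

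The second answer is rarity, and it also stands. Protocol 3.1 puts typical involvement at 80-90% BSA. A foot-only subject needs all six back, arm and leg sites below Grade 2.

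A reader might infer more than the documents support:

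- *Flexural disease opens the same gap.* Protocol 1.1 calls the ichthyosis "particularly prominent in flexure areas", but the same sentence says that it involves much of the body surface. Flexures have no line on the VIIS form, so they yield no VIIS grade with which to meet criterion 3.
- *The subject dilutes the result whatever is done.* A subject without an endpoint adds no value to the mean. SAP 8.5 plans no imputation, although that SAP covers Part 1 only. Dilution arises only if the subject is scored at a site outside the definition.
- *One such subject sinks the 0.5 midpoint requirement in Protocol 10.4.* That needs the other 19 to average exactly 0.5. At the 0.7 seen in the Phase 2 study (on a different scale, the ISS), the mean would be 19 × 0.7 / 20 = 0.665, which passes.
- *The 50% responder requirement becomes harder than if the subject were left out.* Ten responders are needed from the other 19 in both cases, since 9/19 = 47% falls short.
- *Part 1 needs its own entry criterion for extent of disease.* Protocol 5.6 already makes the Investigator identify the initial area of roughly 20% BSA at Grade 2 or higher.

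**Conclusion.** The mismatch is real but small. As written, criterion 3 admits a subject with Grade 2 scaling only on the dorsal foot, and that subject has no valid target efficacy area. No rule stops randomisation. Part 2 matters most, because the efficacy claim rests on it alone (Protocol 10 and 10.4) and its treatment area gives no indirect check.

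The cost per affected active subject is about 1 percentage point of power at SD 0.6 or 2 points at SD 0.7 if the subject is lost. It is about 2 or 3 points if the subject is scored at a Grade 0 site. This rests on the protocol's assumptions (mean change 0.5, 20 active subjects) and on an assumed count of one. Under 2:1 allocation about a third of such subjects would receive vehicle and would not touch the within-group test. The case for changing the text is that the rule can admit an unevaluable subject into a very small trial and is easily corrected, not that a large loss is likely.

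**What to change.** Reword criterion 3 in the synopsis and in Protocol 4.1 along these lines: *VIIS scaling Grade 2 or higher on at least one of upper back, upper arm or lower leg/shin (dorsal foot does not qualify).* Confirm it at the existing Baseline eligibility review, from the VIIS scores taken that day, before randomisation.

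The benefit is mainly for Part 2: SAP 8.6 describes Part 1 delays and treatment interruptions in the past tense, so that part was already under way.

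The cost is one amended criterion and no new assessment. The downside is that an occasional foot-only subject is excluded, who could not have supplied a valid primary endpoint.
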